5.10.2 Criteria for Suspending/Stopping Overall Study

In case of a recurring system malfunction or a severe hypoglycemia event or severe hyperglycemia event during closed loop control (as defined in Section 5.1) that is thought to be device-related (either due to excess insulin administration or suspension due to system malfunction) that occurs in more than two (2) subjects, the overall study will be suspended while the problem is diagnosed. The study may resume if the underlying problem can be corrected by a protocol or system modification that will not invalidate the results obtained prior to suspension.

An instance of severe hypoglycemia or hyperglycemia as defined in section 5.1 will result in DSMB review of the data to determine whether the event was triggered by the system or not and whether it is safe to proceed. The currently-enrolled subjects will continue use of the system during this time unless the DSMB determines it is unsafe for them to do so.

Chapter 6 STATISTICAL CONSIDERATIONS

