1.5.2 Protocol Summary

For the proposed studies, the AP system will be deployed with different functionalities at different stages of the trial, resulting in variation in what the subject will be responsible for and what the system will drive. A trial outline is contained in Figure 1 and visits detailed in Figure 5. **Study Phases without the AP system**

CGM Run-in Phase: Study participants will begin with a maximum 2 week run-in period during which they will have a CGM (i.e. sensor-augmented pump therapy or CGM+CSII) but otherwise be on their usual diabetes management with respect to BG monitoring, pump basal rates, insulin-to-carbohydrate ratios and correction factors. This is necessary because some of the study participants will not have had experience with CGMs in the past.

Study Pump Run-in Phase: All subjects will have a run-in period on the study pump of up to two week duration. Subjects who have had prior experience with the study pump may either skip this run-in phase or may require a shorter run-in period depending on their proficiency with the study pump.

Sensor-Augmented Pump (SAP) Therapy: During this phase, the subject is on the study CGM and their personal insulin pump. There are no predictive or control algorithms. The subjects will administer basal and bolus insulin using their usual home insulin parameters.

Study Phases with the AP System

AP system Run-In Phase: Subjects who have not had recent use of the system (more than approximately 2 weeks of use in the past 6 months or more than 2 months of use in the past year) will complete an up to 2-week home use period with the full system in pump only (open loop) configuration where no closed loop algorithms are activated. Subjects who have had prior experience with the system as defined above will not be required to do Visit 5.

USS+SAP (d): USS Virginia plus SAP during the day (d). Subjects will be using the study pump and CGM with the AP system in Pump mode (open loop only, no closed loop algorithms running). The subject will activate the USS Virginia Closed-Loop Control as early as pre-dinner but is expected to activate CLC by bedtime. The subject will continue in Closed-Loop Control until the time of awakening in the morning. The USS will monitor CGM and insulin-on-board data and predicts the patient's risk of hypoglycemia and adjust insulin delivery accordingly.

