3.10 Study Procedures during USS + SAP(d) and USS + CLC(d)

The subject will be wearing the study CGM, the study pump and utilizing the AP system for 8 weeks. Subject will be doing fingerstick testing using their personal glucometer or study provided glucometer.

For USS + SAP(d): The subject will be instructed to activate closed-loop operation each evening any time between just before eating dinner and prior to bedtime. The subject will be instructed to switch back to open-loop mode upon waking up in the morning.

For USS +CLC(d): The subject will be instructed to remain in closed-loop operation for 24 hours.

While using the closed loop system, the subject will be instructed to avoid deviating from his/her regular daily routine in regards to diet and exercise and to maintain his or her usual sleep schedule during the course of the study. The subject will specifically be asked to avoid consuming more than 3

alcoholic drinks in any one day. The subject will also be instructed to avoid use of closed-loop mode during periods of illness with an elevated temperature >101.5 degrees Fahrenheit, periods of significant illness, or during periods of use of medications such as epinephrine for the emergency treatment of a severe allergic reactions or asthma attack in addition to use of oral or injectable glucocorticoids. The subject will be asked to put the system in exercise mode when engaging in strenuous exertion.

The total duration during each of these phases will be 8 weeks of AP system use regardless of whether CLC was activated or not. If a subject was off the system entirely and unable to use the system (e.g. in Stopped Mode) on one or more days due to illness or other factors such as extended travel, the use period may be extended at investigator discretion to obtain 8 weeks of use.

3.11 Monitoring when the AP system is in Use during Visit 5, USS + SAP(d) and USS + CLC(d)

Throughout the study, the study subject will be given contact information for study team members and can contact the study team at any time.

During the first use of the system at visit 5 and following completion of Visit 5 (second phase for Group A and first phase for Group B), the following procedures will be in place:

- The study team will contact the subject daily for the first week.
- The study team will review the Remote Monitoring System once daily for the first week (if using inControl).

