4.2 System Details

The study system will function in different operational modes in the proposed study: Stopped, Pump, and Closed-Loop. Pump mode will be referred to throughout this protocol and consistently means the delivery of preprogrammed basal rates (Open-Loop) regardless of the system being used. In Closed-Loop mode, basal delivery can be attenuated or increased by the control algorithms.

For inControl system only: If the system malfunctions but the system can still communicate with the pump, the system will fail safe to Pump mode so that the user will continue to receive basal insulin under the direction of the system. If there is a malfunction in which the system cannot communicate with the pump, the system will fail safe to Stopped mode. If the system is in Stopped mode and the Roche pump is being used, the user will begin receiving basal insulin from the pump without any direction from the AP system within a short period of time.

The table below summarizes the system modes for inControl and some of the functionality available in each mode:

Mode	Overview	CGM data?	Basal Insulin delivered via AP?	Bolus Insulin delivered via AP?	Hypo-/Hyper Glycemia Alerts?	Data Transfer to Remote Server to allow monitoring?
"Stopped"	System comes online in Stopped mode and awaits user action. User may switch the system into Stopped mode at any time.	No	No	Νο	No	No
"Pump"	Emulates traditional insulin pump behavior of open-loop basal insulin delivery according to preprogrammed pattern; used instead of Closed-Loop mode when replacing CGM sensor	Yes, if available	Yes, identical to preprogrammed pattern	Yes, but only user- requested manual boluses; no automated boluses	Yes	Yes
"Closed Loop"	Control algorithm determines appropriate automated insulin delivery. Can only activate if CGM data is available.	Yes	Yes, according to algorithm based on preprogrammed pattern attenuated or increased when needed	Yes, automated boluses if algorithms are active, and user- requested manual boluses at any time	Yes	Yes

Table 1: Basic functionality of system in each operational mode

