4.4 Safety Measures

4.4.1 Safety Measures of Insulin Dosing

In Closed-Loop mode, all dosing is supervised by a dedicated safety supervision system module and insulin correction for meal boluses must be manually confirmed. In Pump and Closed-Loop mode:

- Bolus size is checked by the algorithm to ensure it is smaller than the maximum bolus that the pump can handle;
- For inControl, switching to "Stopped" mode includes a 'cancel all' delivery message to the pump so that any active but incomplete bolus is cancelled with the Roche Accu-Chek pump.
- All insulin requests are made in the form of boluses or temporary basal rate changes; this ensures that in case of a system crash or pump disconnection, no request has permanence;
- Users will be able to monitor delivered insulin in the plots menu on the phone which is available from the main screen in any operating mode. The remote monitoring displays the delivered insulin and total insulin delivered during the past 4 hours via the web interface;
- It is important to note that IOB constraint is an internal safety feature of the closed-loop system. It is not read from the pump or any other external source. The IOB in the system is computed by the system using a model of the transport and clearance of insulin from the subcutaneous infusion site to the circulation, and is intended to prevent insulin overdose.

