4.4.5 CGM Sensor Failure

If the CGM signal becomes unavailable for an extended period of time during Closed-Loop mode, the system will revert to Pump mode.

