5.1 Definition

A reportable adverse event is any untoward medical occurrence or any unexpected medical occurrence in a study subject.

Hypoglycemic events are recorded as Adverse Events if the event required assistance of another person due to altered consciousness to actively administer carbohydrate, glucagon, or other resuscitative actions. This means that the subject was impaired cognitively to the point that he/she was unable to treat him or herself, was unable to verbalize his or her needs, was incoherent, disoriented, and/or combative, or experienced seizure or coma. These episodes may be associated with sufficient neuroglycopenia to induce seizure or coma. If plasma glucose measurements are not available during such an event, neurological recovery attributable to the restoration of plasma glucose concentration.

Hyperglycemic events are recorded as Adverse Events if evaluation or treatment was obtained from a health care provider or if the event involved diabetic ketoacidosis (DKA), as defined by the Diabetes Control and Complications Trial (DCCT), and had all of the following:

- Symptoms such as polyuria, polydipsia, nausea, or vomiting;
- Serum ketones or large/moderate urine ketones;
- Either arterial blood pH <7.30 or venous pH <7.24 or serum bicarbonate <15; and
- Treatment provided in a health care facility

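### Read literally, the overall suspension rule in 5.10.2 does not count a severe event caused by automated insulin if it begins after closed loop has ended

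*Combined protocol and SAP*

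**What the plan says.** The first paragraph of 5.10.2 has two triggers. One is a recurring system malfunction, with no limit on operating mode. The other is "a severe hypoglycemia event or severe hyperglycemia event during closed loop control (as defined in Section 5.1) that is thought to be device-related". The rule names two device causes, too much insulin given or delivery suspended through a malfunction. Suspension follows when more than two subjects are affected. The second paragraph sends any severe event meeting Section 5.1 to the DSMB, whatever the mode.

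On operating modes, Section 4.2 says: "The study system will function in different operational modes in the proposed study: Stopped, Pump, and Closed-Loop". For USS+SAP(d), Section 1.5.2 says "The subject will continue in Closed-Loop Control until the time of awakening in the morning", and Section 3.10 says "The subject will be instructed to switch back to open-loop mode upon waking up in the morning". Closed loop can also end without the subject acting. Section 4.4.5 states: "If the CGM signal becomes unavailable for an extended period of time during Closed-Loop mode, the system will revert to Pump mode".

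Section 5.1 defines severe hypoglycemia by the need for another person's help. For high glucose it says "Hyperglycemic events are recorded as Adverse Events if evaluation or treatment was obtained from a health care provider", or if the event involved DKA. Neither definition has a time window or refers to mode.

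Rule 2 in 5.10.1, for the individual subject, is built differently. There the closed-loop wording qualifies the insulin delivery, and the event only has to be related to that delivery.

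**The concern.** The severe-event trigger asks two questions: did the device cause the event, and was the subject in closed loop at the time? The two can have different answers, because insulin keeps acting after it is given. The protocol recognises this in Section 4.4.1: "The IOB in the system is computed by the system using a model of the transport and clearance of insulin". Section 4.1 lets the algorithm raise basal delivery to as much as three times the programmed rate. Once the subject switches to Pump mode, basal returns to the programmed pattern (Section 4.2). Automated attenuation then stops while insulin already delivered is still acting.

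A severe morning hypoglycemia caused by overnight automated dosing could therefore begin after the switch. It would have a cause the rule names and still fall outside its wording. The same could happen after a reversion to Pump mode for lost CGM signal. What is at stake is a preset trigger that may not fire at the number of device-caused cases it was meant to act on.

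**Working it through.** The plan gives no derivation for the threshold and no severe-event rate, so there is no figure to reproduce. The check compares the texts and then does a count.

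**1. What the timing phrase can mean**

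- *Operating state.* Sections 1.5.2 and 3.10 describe closed loop in USS+SAP(d) as a state that ends on waking, and Section 4.2 separates it from Pump mode. On this reading, an event that begins after the switch is not counted.
- *Whole AP period or system.* Section 3.5 speaks of a first session of closed-loop control, and Section 1.4 and the Chapter 4 title use the term for the system as a whole. On this reading little or no gap remains.
- *Qualifier of hyperglycemia only.* Post-switch hypoglycemia is then counted. This is the weaker parse, because the cross-reference to Section 5.1 that follows the phrase must serve both event types. What would be left out is late hyperglycemia from a malfunction that is not judged recurring.

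Section 5.10.2 does not say which reading applies.

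**2. The same event under the two rules.** Take a severe hypoglycemia that begins after the morning switch and is judged to be caused by overnight automated insulin.

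- Rule 2 in 5.10.1: related to automated delivery in closed loop, so it counts toward that subject's two episodes.
- Severe-event trigger in 5.10.2, read literally: the subject is no longer in closed loop, so it does not count toward suspension.
- Second paragraph of 5.10.2: it goes to the DSMB.

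**3. Effect on the count.** More than two subjects means at least 3. Suppose 3 subjects each have one device-caused severe event, and k of these begin after closed loop has ended.

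- Count by cause = 3 for every k, so suspension fires.
- Literal count = 3 − k. For k = 1, 2, 3 this is 2, 1, 0. All are below 3, so suspension does not fire.
- DSMB reviews = 3 for every k, one per event.

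**4. How often the setting arises.** Both groups have two USS+SAP(d) periods of 8 weeks among three AP periods. That is 16 of 24 AP weeks, or 2 × 8 × 7 = 112 planned morning switches per completer. This counts opportunities only and says nothing about how often a severe event follows.

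**5. What cannot be computed.** The chance that the trigger is missed needs two inputs: the per-subject probability of a device-caused severe event, and the share of such events that begin after closed loop. The documents give neither. Section 4.4.1 says "The remote monitoring displays the delivered insulin and total insulin delivered during the past 4 hours via the web interface", but that is a display window and not a stated duration of insulin action, so it cannot stand in for a carry-over period.

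**The case against.** The strongest reply is that the protocol usually adds the word mode when it means the operating mode, and 5.10.2 does not. Together with the broader uses in 3.5, 1.4 and Chapter 4, this makes the whole-period reading a fair one. That stands. A reader might infer that the plan definitely excludes post-switch events. The documents show only that a literal reading does so and that the rule does not settle the matter.

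The second reply is that oversight does not depend on the count. Every severe event, from the first and in any mode, goes to the DSMB, which judges whether the system triggered it and can stop use of the system. Section 5.8 adds that the board's stopping rules will be set out separately. This also stands. A reader might infer that post-switch events escape safety review, and that would be wrong. The remaining difference is that subjects stay on the system during DSMB review unless the board acts, whereas the count suspends the study automatically.

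Third, the case is narrow. The subject must wake, be able to switch, and only then become incapacitated. An event before the switch is counted, and hypoglycemia alerts stay active in Pump mode. The same malfunction in three subjects would naturally be recurring and enter through the other trigger. That trigger need not, however, catch overdosing by a system that works as designed.

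Finally, simply deleting the timing phrase would go too far. Device-related is not limited to the controller, so pump problems in daytime Pump mode or in a SAP period could enter the count. This is right, and it shapes the fix.

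**Conclusion.** The point holds as a gap on a literal reading. If the timing condition refers to the operating state, a severe event caused by automated insulin is left out of the suspension count when it begins after the morning switch or after a CGM-loss reversion. One such case among three is enough to keep the literal count at 2.

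The consequence is modest. Only the automatic suspension is affected. DSMB review, the recurring-malfunction trigger and the individual rule are untouched. The conclusion rests on the operating-state reading, and on insulin given in closed loop still acting after it ends, which the protocol's own insulin-on-board model implies but does not quantify for this purpose. No probability of a missed suspension is claimed, since any figure would only reflect assumed rates. The severity is the lowest: a cheap improvement to a safety rule whose own test is already causal.

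**What to change.** In the severe-event trigger of 5.10.2, replace the closed-loop timing condition with the attribution used in rule 2 of 5.10.1. The trigger would then require a severe event under Section 5.1 that is thought to be device-related and is related to automated insulin delivery in closed loop, whether the event begins while closed loop is running or after it has ended.

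Keep the two named causes, so that suspension through malfunction remains covered. Leave unchanged the threshold of more than two subjects, the recurring-malfunction trigger, the DSMB paragraph and 5.10.1. The link to automated delivery keeps out pump events from open-loop or SAP use that have nothing to do with the algorithm.

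The cost is one clause in a protocol amendment, a few more causation judgements and possibly an earlier suspension. The added work is small, because the DSMB already has to judge causation for every severe event.

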6.1 Analysis Plan

Statistical Analysis: The overall analysis will follow Intention-to-treat approach and will use Generalized Linear Mixed Models (e.g. those available in IBM SPSS) including fixed factors following the factorial designs presented in study figure for the specific aims listed below, and random effects reflecting patients' attrition rate.

Metrics:

- (i) Five HbA1c determinations approximately 10 weeks apart;
- (ii) Eight-week sequences of CGM data accompanied by BG self-monitoring readings and recording of the timing of events such as meals and exercise through the GUI
- (iii) Psychometric questionnaires administered concurrently with HbA1c, and
- (iv) Individual structured interview and qualitative/quantitative technology acceptance assessments. CGM data will be used to compute established metrics of risk for hypoglycemia, e.g. the Low BG Index (LBGI), glucose variability, and BG dynamics, as presented in our review of statistical tools for CGM data analysis.

Primary Hypothesis by Specific Aims of the Study

Specific Aim 1: Overnight CLC achieved by USS+SAP(d) will be superior to SAP alone in terms of: (1) Improved HbA1c without increasing the risk for hypoglycemia; (2) Reduced incidence and risk for hypoglycemia overnight, and (3) Reduced fear of hypoglycemia and improved diabetes quality of life scores.

Specific Aim 2: CLC during the day achieved by USS+CLC(d) will preserve the benefits of USS+SAP(d) and will be superior to USS+SAP(d) in terms of: (1) Increased time within target range of 70-180mg/dl during the day; (2) Reduced risk for hypoglycemia during and after exercise, and (3) Reduced postprandial glucose variability.

Specific Aim 3: CLC system acceptance evaluated by an individual structured and technology acceptance scores will be: (1) Superior, for USS+SAP(d) compared to SAP alone, i.e. adding USS overnight will increase patients' acceptance of CLC, and (2) Marginally inferior, for USS+CLC(d) compared to USS+SAP(d); i.e. some patients would prefer SAP alone during the day due to perceived increased system complexity.

Primary Outcomes

Specific Aim 1: The **primary outcome** is improvement in diabetes control on USS+SAP(d) vs. SAP alone as defined by reduced risk for hypoglycemia (Time <70 mg/dL by CGM) without increase in HbA1c. Repeated Measures ANOVA with covariate will assess this effect. Inversely, comparing HbA1c with covariate overnight Time <70 mg/dL by CGM will address SA1-2, while comparing the psychometric questionnaire scores pre-post treatment will address SA1-3.

Specific Aim 2: The **primary outcome** is improved time within the target range of 70-180mg/dl during the day on USS+ CLC(d) vs. USS+SAP(d). Repeated Measures ANOVA following the study design outlined will assess this effect. SA2-2 will be addressed

comparing frequency of hypoglycemia within the post-exercise periods recorded by the system; SA2-3 will be addressed using Variability-Grid Analysis, and SA-4 will be addressed by a sub-analysis limited to those who did not achieve HBA1c≤7.5% during the first 3 months of the study.

Specific Aim 3: will be addressed by comparing structured interviews and technology acceptance scores along the two sequences of treatment modalities specified in the study design: treatment escalation for Group A and de-escalation for Group B. Analyzing the random effect of patient attrition will shed additional light on system acceptance.

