The subject must be able to complete system-related tasks independently to be eligible to continue in the study.

3.6 Visit 5 - AP System Run-In phase: Home Use in Pump Only (Open Loop) Configuration

Eligible subjects who have not had recent use of the system (more than ~2 weeks of use in the past 6 months or more than ~2 months of use in the past year) will complete up to 2-week home use period with the full system in pump only (open loop) configuration where no closed loop algorithms are activated. Subject will be instructed not to start closed loop during this run-in phase. Subjects who have had prior experience with the AP system as defined above will not be required to do Visit 5. Subjects who are demonstrating proficiency, as determined by the study physician, may have a shorter open loop run-in phase with a minimum of 5 days duration Criteria for proficiency is listed in section 3.11.

For the inControl system, remote monitoring will be available during this period for the purposes of data collection and ad hoc assessment of system performance by study team. The study team will be available for the subject to contact during this phase. Study staff will contact the subject and review data on the Remote Monitoring once daily. The subject may contact the study staff at any time.

For the Tandem-G6 system, remote monitoring will not be available. Study staff will contact the subject daily to assess difficulties with the use of the system. The subject may contact the study staff at any time. If the study team requires additional information, the subject may be asked to upload the pump at home so that the study can review data on the t:connect website.

3.7 Visit 6 + Visit 7 + Visit 8 Washout Following Completion of the Each Study Phase

At the completion of the each phase of the study, subjects will have up to a two week washout prior to proceeding to the next phase.

First Phase: Group A 8 weeks of SAP; Group B 8 weeks of USS +SAP(d) Second Phase: Group A 8 weeks of USS +SAP(d); Group B 8 weeks of USS + CLC(d) Third Phase: Group A 8 weeks of USS + CLC(d); Group B 8 weeks of USS +SAP (d) Fourth Phase: Group A 8 weeks of USS + SAP(d); Group B 8 weeks of SAP

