6.2 Sample Size

Sample Size Determination is based on our pilot studies of overnight CLC. We conservatively estimate that the effect size of USS+SAP(d) vs. SAP will be $f \ge 0.2$. Power calculations (G*Power 3) assuming $\alpha = 0.01$, 90% power, correlation of 0.4 between the repeated measures, and attrition of up to 31% yield a sample size of **N=110** subjects to be randomized at baseline, with N=76 subjects completing the study. For SA2 using USS+CLC(d), our pilot data with this same system during the day indicate a larger effect size f=0.3. For SA-3, the expected effect size is f=0.35-0.4 based on our previous interviews. Thus, a sample size that is adequate for SA-1 will have adequate power to address SA-2 and SA-3 as well.

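### Section 6.1 names both a mixed model and repeated-measures ANOVA for the primary outcomes, without saying which governs; the mixed model has no subject effect, and no rule covers a missing phase

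*Combined protocol and SAP*

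**What the plan says.** Section 6.1 opens with a general statement: "The overall analysis will follow Intention-to-treat approach and will use Generalized Linear Mixed Models", "including fixed factors following the factorial designs presented in study figure". It ties this to the specific aims that follow. The random part of the model is described only as "random effects reflecting patients' attrition rate".

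Under Primary Outcomes, the same section names a different method for each of the first two aims. For Aim 1 (CGM time below 70 mg/dL without an increase in HbA1c): "Repeated Measures ANOVA with covariate will assess this effect". For Aim 2 (daytime time in range): "Repeated Measures ANOVA following the study design outlined will assess this effect". For Aim 3 the attrition term returns with another purpose: "Analyzing the random effect of patient attrition will shed additional light on system acceptance".

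Section 3.7 gives the phase order. It ends: "Fourth Phase: Group A 8 weeks of USS + SAP(d); Group B 8 weeks of SAP". Group A has SAP in phase 1.

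Section 6.2 reads "attrition of up to 31% yield a sample size of" 110 randomised, with 76 completing; section 1.5.1 repeats both figures. Section 3.10 lets a phase be extended for days off the system. No section says how to analyse a phase that is abandoned or never started.

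**The concern.** Two analysts could follow section 6.1 faithfully and analyse different subjects with different models. Classical repeated-measures ANOVA needs every repeated measure and drops a subject with a missing phase. A mixed model with a subject effect keeps the phases that were observed. Only the second fits the stated intention-to-treat approach.

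The mixed model as described does not settle the matter. A random effect belongs to a grouping unit such as the subject; attrition is something that happens to subjects after randomisation. No term or covariance structure is given that would link the phases of one subject.

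For Aim 1 the loss can also be uneven. A Group B subject who leaves before phase 4 has no SAP data, whereas a Group A subject has both SAP and USS+SAP(d) after phase 2. Such exits are foreseeable. As section 3.2 is written, randomisation precedes the run-ins. Section 3.3 lets staff discontinue a subject after the CGM run-in, and section 3.5 makes continuation depend on mastering the system. Group B meets that training before its first phase, Group A after its SAP phase.

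**Working it through.** **1. The plan's own sample size.** Inputs from section 6.2: f = 0.2, alpha = 0.01, power 90%, correlation ρ = 0.4, attrition 31%. The standard repeated-measures F test has noncentrality λ = f²·N·m/(1 − ρ), with m − 1 and (N − 2)(m − 1) degrees of freedom for two groups. The number of measures m is not stated, so I tried several:

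| m | N for 90% power | Power at N = 76 |
|---|---|---|
| 2 | 115 | 0.704 |
| 3 | 90 | 0.829 |
| 4 | 75 (76 in equal groups) | 0.909 |
| 5 | 64 | 0.954 |

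For m = 4, λ = 0.04 × 76 × 4/0.6 = 20.27. Only m = 4 gives the plan's 76. Attrition then gives 76/0.69 = 110.1, and 110 × 0.69 = 75.9. The sample size therefore matches a four-measure ANOVA on complete subjects. This is inferred from the match, not stated. (Section 2.1 gives 64 completers; I use the 76 of sections 1.5.1 and 6.2.)

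**2. Who is left out.** An ANOVA over all four phases leaves out 110 − 76 = 34 at the attrition ceiling. If only the two compared modalities must be observed, the count depends on timing. Assume 55 per arm, 17 dropouts per arm, all leaving between phases. Subjects left out (Group A + Group B):

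| All dropouts leave | Aim 1 | Aim 2 |
|---|---|---|
| before phase 1, or after phase 1 | 17 + 17 = 34 | 17 + 17 = 34 |
| after phase 2 | 0 + 17 = 17 | 17 + 0 = 17 |
| after phase 3 | 0 + 17 = 17 | 0 |

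For Aim 1, Group B loses all 17 whatever the timing; Group A loses between 0 and 17.

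**3. Precision for Aim 1.** Assumptions: outcome SD 1, equal correlation 0.4 between phases, sequence as a fixed effect, 17 dropouts per arm unrelated to outcome. Sequences are SAP, USS+SAP(d), USS+CLC(d), USS+SAP(d) in Group A and USS+SAP(d), USS+CLC(d), USS+SAP(d), SAP in Group B. Standard errors by generalised least squares. A hand check for completers without period: USS+SAP(d) is observed twice and SAP once, so the variance is (1 − 0.4)(1 + 1/2)/76 = 0.9/76 = 0.01184, and the SE is 0.1088.

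| Data used | SE, no period | SE, with period |
|---|---|---|
| 76 completers | 0.1088 | 0.1257 |
| All phases, all leave before phase 1 | 0.1088 | 0.1257 |
| All phases, all leave after phase 1 | 0.1043 | 0.1194 |
| All phases, all leave after phase 2 | 0.0995 | 0.1176 |
| All phases, all leave after phase 3 | 0.0988 | 0.1163 |
| All phases, dropout evenly spread over 0 to 3 completed phases | 0.1025 | 0.1194 |

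With the same terms, using all phases lowers the SE by 0 to 9% without period (0.0988/0.1088 = 0.908) and by 0 to 7.5% with period (0.1163/0.1257 = 0.925). Adding period raises it by about 16% (0.1257/0.1088 = 1.155; 0.1194/0.1025 = 1.165).

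**4. Power for Aim 1.** Power ≈ Φ(δ/SE − 2.576), two-sided alpha 0.01. How f = 0.2 maps to a difference is my assumption: 0.40 SD for two means (f = δ/2), or 0.462 SD for four phases where only SAP differs (f = δ·√(0.25 × 0.75)).

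| Analysis | 0.40 SD | 0.462 SD |
|---|---|---|
| Completers, no period | 86% | 95% |
| Completers, with period | 73% | 86% |
| All phases, evenly spread, with period | 78% | 90% |

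Example: 0.40/0.1194 − 2.576 = 0.774, and Φ(0.774) = 0.78.

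**The case against.** The strongest reply is that there is no conflict. The opening statement of section 6.1 covers the specific aims, so ANOVA may only name the within-subject comparison made inside the mixed model. The Aim 1 wording leans that way: its covariate appears to be HbA1c, which is measured repeatedly, and a phase-specific covariate suits a mixed model better than classical ANOVA. This is a fair reading. It stands as a possibility, but no sentence states it, and the sample size matches the ANOVA.

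A reader might infer four stronger things that the documents do not support:

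- *That the plan ignores within-subject correlation.* Repeated-measures ANOVA treats subject as a block. The gap is in the mixed model's specification.
- *That the attrition effect is offered as a correction for dropout.* Section 6.1 does not claim this; its only stated use is to inform acceptance under Aim 3. That aim is legitimate, and another summary can serve it.
- *That losing 34 subjects is an unplanned loss of power.* Section 6.2 already sizes the trial on 76 completers. The issue is departure from intention to treat and possible imbalance by sequence.
- *That the result will be biased.* The calculation takes dropout as unrelated to outcome and so measures precision only. The documents give no dropout timing and no run-in failure rates. Because Visits 2 and 3 may coincide with screening, some training may take place before randomisation.

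**Conclusion.** The point holds as an unresolved choice of primary analysis, not as a proven contradiction or a proven bias. Section 6.1 does not say which method governs Aims 1 and 2, gives its mixed model no usable random effect, and has no rule for a missing phase. If classical ANOVA is run as written, up to 34 of 110 randomised subjects are excluded at 31% attrition, against the stated intention-to-treat approach. For Aim 1 the exclusion can fall more heavily on Group B.

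The precision argument is modest and can change sign. If period is already in the model, moving from completers to all phases raises Aim 1 power from 73% to 78% (0.40 SD, evenly spread dropout). If it is not, the recommended model lowers power from 86% to 78%. The fixed factors are defined by a study figure not available here, so which case applies cannot be determined. These figures rest on equal correlation of 0.4, 17 dropouts per arm, dropout unrelated to outcome, and the assumed mapping from f to a mean difference.

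This should be fixed before analysis, because the choice determines who is analysed.

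**What to change.** Name one primary model for Aims 1 and 2: a likelihood-based linear mixed model using all observed phases of every randomised subject with at least one phase. Include fixed treatment (three modalities), period and sequence, after confirming which of these the study figure already contains. Include a random subject effect, and state the missing-at-random assumption. Say whether the Aim 1 covariate is kept. Because this set can be smaller than all randomised subjects, report by group how many contribute no phase.

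Replace the attrition random effect, in both places in section 6.1, with discontinuation reported by the modality in use; this still serves Aim 3. Keep the completer ANOVA as a sensitivity analysis.

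The cost is plan wording and some programming, with no new data. If period is new to the model, the standard error rises by about 16%. The net Aim 1 value is then about 10% above completers without period (0.1194/0.1088 = 1.097). Section 6.2 should restate power for the model chosen.
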